9.1.2 Schedule of Assessments

The schedule of assessments is presented in Table 9-1.

Table 9-1 Schedule of Assessments

Visit	Acute Exacerbation Phase									Stabilisation phase			
	1	2	3	4	5	6	7	8	9	10	11	12	
	Screening ¹	Randomisation/ Baseline ¹ Day 1	Day 2	Day 3	Day 4	Day 5	Day 6	Day 7	Day 10 (± 1 day)	Day 14 (± 1 day)	Week 8 (± 3 days)	Week 12 (± 3 days)	Week 26 (± 3 days)
Written Informed consent	X												
Demographics	X												
Medical history including current medical conditions ¹⁷	X												
Smoking history	X												
Inclusion/exclusion criteria	X												
Full physical examination ^{2, 15}	X	X	X	X	X	X	X	X	X	X	X	X	X
Vital signs ²	X	X	X	X	X	X	X	X	X	X	X	X	X
12-Lead ECG ^{3,4,7}	X	X	X	X	X	X	X	X	X	X			
Assessment of inflammation of cervix and vagina ¹⁶	X							X		X			
Pregnancy test ⁴	X										X	X	X
Clinical laboratory tests ^{2,5,6} (haematology, blood chemistry and urinalysis laboratory assessments)	X	X		X		X		X	X	X	X	X	X
PK assessment ⁷		X		X		X							
PFT (Spirometry)	X ^{9,13}	X ^{8,13}	X ⁸	X ⁸	X ⁸	X ⁸	X ⁸	X ⁸	X ⁸	X ⁸	X ^{8,14}	X ^{8,14}	X ^{8,14}
Randomisation		X											
mMRC,		X						X		X	X	X	X

6MWT/BMI ¹⁰										X			
CRQ		X								X	X	X	X
Blood biomarkers ^{6,11}		X	X	X	X	X	X	X	X	X	X	X	X
Exploratory composite scale										X	X	X	X
EXACT-PRO		X	X	X	X	X	X	X	X	X	X	X	X
Study treatment		[REDACTED]											
Adverse events	X	X	X	X	X	X	X	X	X	X	X	X	X
Concomitant medications	X	X	X	X	X	X	X	X	X	X	X	X	X

- 1 Ideally subjects should be screened and randomised and dosed on the same day. There will be no separate Screening Visit as subjects will receive their first dose of study treatment within 24 hours of presenting with an acute exacerbation. Subjects will be eligible only if their treatment (SoC) has been initiated less than 24 hours before Randomisation and dosing (Day 1). For screen failures, re-screening may be performed 1 month after complete recovery from a previous acute exacerbation of COPD.

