- 7 There will be sparse PK sampling in all subjects to be taken on any 2 of the 3 dosing occasions (Days 1, 3, or 5): one sample to be taken pre-dose, one sample taken 0-2 h post-dose, one sample taken 4-8 hours post-dose, and one sample no earlier than 12 hours post-dose. ECG will be taken at approximately the same time as with PK sample. ECGs should be taken before the PK sample.

- 8 Spirometry will be taken 'on bronchodilator' and ideally in the morning. For an individual spirometry should be taken at approximately the same time of day (during the acute phase \pm 1 hour and in the stabilisation phase \pm 2 hour window). Ideally this will be taken at least 1 hour after regular long acting bronchodilators and 30 minutes after short acting bronchodilator medication. Time of last short and long acting bronchodilators will be documented.
- 9 Spirometry at Screening should be performed 'on bronchodilator'. This will be taken after any regular long acting bronchodilator administration and 30 minutes after short acting bronchodilator medication.
- 10 Perform BMI and 6MWT at Day 14. BODE will then be calculated.
- 11 Please refer to the Laboratory Manual for clarification of whether the biomarker is to be analysed in either serum or plasma.
- 12 If the subject is discharged before Day 7, they will return to the hospital daily for assessment.
- 13 If screening and Day 1 occur on different days spirometry will be repeated on day 1 before dosing with study treatment and result obtained on day 1 may be used as baseline.
- 14 If historical spirometry data within last 12 months does not include pre and post SABA value this should be obtained during the stabilisation phase, for demographic purposes.
- 15 Physical examination at screening should include a minimum of chest, cardiovascular and abdominal examination. At all other time points a minimum of chest auscultation is required. Additional examination is at the discretion of the Investigator as indicated by the subjects' clinical condition.
- 16 A gynaecological history should be taken (from females only) with subjects specifically asked about vaginal bleeding, discharge or pain. Any new vaginal bleeding (other than normal menstruation), vaginal discharge or pain after dosing should be investigated by vaginal examination and any required specialist assessment.
- 17 Document in eCRF which symptoms of the acute exacerbation are present out of increased sputum, increased cough and increased dyspnoea.

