9.1.3 Study Assessments

9.1.3.1 Screening (Visit 1)

Subjects will be screened on the day that they present with an acute exacerbation (Day 1); there will be no separate Screening Visit as subjects will receive their first dose of study treatment within 24 hours of presenting with an acute exacerbation. Subjects will be eligible only if their treatment (SoC) has been initiated less than 24 hours before Randomisation and dosing (Day 1). For screen failures, re-screening may take place 1 month after complete recovery from a previous acute exacerbation of COPD.

The following procedures/assessments will be done:

1. Collection of the written informed consent signed by the subject, after the study has been fully explained by the investigator. The investigator or his/her designee should provide enough time and opportunity to inquire about details of the study and to decide whether or not to participate in the study, however respecting the study timelines defined in the inclusion and exclusion criteria
2. Collection of demographic data and medical/surgical/psychiatric history, including smoking history and gynaecological history (females)
3. Exacerbation assessment to verify a documented history of at least one exacerbation in the 12 months preceding Screening
4. Verification that spirometry has been performed within the last 12 months and outside of an exacerbation
5. Physical examination, including vital signs (body temperature, RR, pulse rate, blood oxygen [measured using a pulse oximeter], systolic and diastolic blood pressure), height, and weight
6. 12-lead electrocardiogram (ECG); recorded after 10 minutes at rest
7. Urine and serum pregnancy test, women of child-bearing potential only
8. Blood sample for clinical laboratory tests (haematology and biochemistry) to be taken at least 6 hours after SABA (whenever possible; times of sample collection and SABA intake must be recorded), after 8 hours of fasting (whenever possible), and after completion of ECG and vital signs (body temperature, RR, pulse rate, systolic and diastolic blood pressure). These clinical laboratory tests will be performed both at the local and central laboratory to confirm eligibility for Randomisation
9. Urinalysis (specific gravity, pH, protein, glucose, blood)
10. 'On bronchodilator' spirometry. This will be taken after regular long acting bronchodilators and 30 minutes after short acting bronchodilator
11. Confirm inclusion and exclusion criteria

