death will be summarised by SOC and PT for each treatment regimen and overall (number and percentage of subjects experiencing at least one AE per PT as well as the number of observed events per PT). All TEAEs will also be summarised separately by maximum severity grade for each SOC and PT and by relationship to study medication for each SOC and PT. These summarisations of TEAEs will also be provided for TEAEs occurred during the Acute Exacerbation Phase and for TEAEs occurred during the Stabilisation Phase separately.

A table presenting the number and percentage of subjects with at least one AE and the number of AEs for the most common treatment-emergent AEs (reported in $\geq 1\%$ of patients in any treatment regimen) will be provided. PTs will be used for tabulation, sorted by decreasing overall frequency. This table will also be presented for TEAEs occurred during the Acute Exacerbation Phase and for TEAEs occurred during the Stabilisation Phase separately.

The number and percentage of subjects with any treatment-emergent pneumonias, pneumonias related to study medication, serious pneumonias, serious pneumonias related to study medication, severe pneumonias, pneumonias leading to permanent discontinuation of study treatment, pneumonias leading to death will be presented by treatment regimen and overall. The number of events will also be displayed. This table will also be presented for treatment-emergent pneumonias occurred during the Acute Exacerbation Phase and for treatment-emergent pneumonias occurred during the Stabilisation Phase separately.

Treatment-emergent pneumonias will be analysed in terms of rate per 1'000 patient per year. The follow-up time (in years) will be calculated using the following formula:

$$(\text{date of last contact} - \text{date of first study treatment} + 1) / 365.25$$

The rate of treatment-emergent pneumonia per 1'000 patient per year will be calculated for each treatment using a weighted approach (which consists of pooling all patients of a treatment regimen and dividing the total number of events by the total follow-up time, multiplying the result by 1000).

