11 APPENDICES

Appendix A – Summary of Protocol Amendments - Key Changes

Amendment	Change	Rationale
Protocol Version 2.0, Amendment 1 (revisions to Protocol Version 1.0)	Added pulse oximeter measurements as part of vital sign measurements to be carried out	At the request of the FDA
Protocol Version 3.0, Amendment 2 (revisions to Protocol Version 2.0)	Laboratory test change: requirement for INR and prothrombin time sampling and testing after Day 14 removed	As the last dose is taken on Day 5, analysis of INR and prothrombin time is only deemed necessary during the Acute Exacerbation Phase
Protocol Version 3.0, Amendment 2 (revisions to Protocol Version 2.0)	Reduction of ECG testing from triplicate to a single test	ECG are no longer required in triplicate by the Central Reader
Protocol Version 3.0, Amendment 2 (revisions to Protocol Version 2.0)	Addition of inflammation of cervix and vagina as an adverse event of special interest	Align with Investigator's Brochure at the request of the UK Regulatory Agency
Protocol Version 4.0, Amendment 3 (revisions to Protocol Version 3.0)	Modification of inclusion criterion 4 to reflect that spirometry in the past 12 months is required but the result does not need to be available before dosing.	Spirometry is being done at screening and this will be used to determine eligibility for the study. Historical data is required for data analysis demography only. If historical values are not available, pre and post bronchodilator spirometry will be conducted during the stabilization phase, for demographic purposes.
Protocol Version 4.0, Amendment 3 (revisions to Protocol Version 3.0)	Modification of inclusion criterion 5 to allow subjects who have given up smoking in the last 6 months into the study.	The impact of smoking cessation within 6 months is not significant to the patient assessment, within the trial.
Protocol Version 4.0, Amendment 3 (revisions to Protocol Version 3.0)	Increase of FEV1 to <65 % of the predicted normal value for inclusion criterion 6.	This will facilitate recruitment of the appropriate population and is not anticipated to adversely impact safety of subjects or efficacy outcomes.

Protocol Version 4.0, Amendment 3 (revisions to Protocol Version 3.0)	Removal of inclusion criterion 7 regarding post-bronchodilator spirometry.	In the acute exacerbation setting it is challenging to conduct pre and post bronchodilator spirometry. Therefore, all spirometry measurements will be performed 'on bronchodilator'.

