Protocol Version 4.0, Amendment 3 (revisions to Protocol Version 3.0)	Modification of spirometry assessment and timings to reflect that all spirometry will be taken at least 1 hour after regular long acting bronchodilator administration and 30 minutes after a short acting bronchodilator rescue medication has been taken. For patients with acute exacerbation it is not practical to have FEV1 after bronchodilator wash out.	It is necessary to standardize baseline and post study drug assessment of spirometry as much as practically possible.
Protocol Version 4.0, Amendment 3 (revisions to Protocol Version 3.0)	Modification to timing of ECG assessments.	BCT197 would not be expected to be present in the body at 8, 12 and 26 weeks post dose and so ECGs at these time points have been removed. Additional ECGs have been added at dosing and PK sample times to increase safety monitoring and to allow for PK/PD analysis of QTc data around the time of maximum concentration BCT197 are included.
Protocol Version 4.0, Amendment 3 (revisions to Protocol Version 3.0)	Collection of baseline information on presence of specific symptoms of acute exacerbation (increased sputum production, increased cough and/or increased dyspnea).	Data required to better characterize the patient population.
Protocol Version 4.0, Amendment 3 (revisions to Protocol Version 3.0)	Addition of theophylline to permitted concomitant medications.	May form part of standard care.
Protocol Version 4.0, Amendment 3 (revisions to Protocol Version 3.0)	Six minute walk test has been reduced to single measurement at end of acute exacerbation.	The expectation is that subjects will be unable to perform this test due to their clinical condition in the early part of the exacerbation. A single measurement at

		day 14 gives adequate data.
Protocol Version 4.0, Amendment 3 (revisions to Protocol Version 3.0)	The composite score has been removed from Baseline Visit.	The composite score detects treatment failure so should not be included at Baseline.
Protocol Version 4.0, Amendment 3 (revisions to Protocol Version 3.0)	Inclusion of vaginal inflammation evaluation (history and if indicated by symptoms, examination).	Included following regulatory agency feedback.

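### Cervical/vaginal inflammation is reported as a percentage of all treated subjects, men included, and its by-phase figures rest on unequal questioning that no table flags

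*SAP*

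**What the plan says.** **Status of the event.** SAP Appendix A records, for protocol V3.0, "Addition of inflammation of cervix and vagina as an adverse event of special interest", at the request of the UK regulator. SAP 4.4 lists it among the safety endpoints. For V4.0, Appendix A adds an evaluation by history, with examination if symptoms call for it, after regulatory feedback.

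**Collection.** In Protocol Table 9-1 the row "Assessment of inflammation of cervix and vagina" is marked at Screening, Day 7 and Day 14. Footnote 16 to that table reads: "A gynaecological history should be taken (from females only) with subjects specifically asked about vaginal bleeding, discharge or pain". It continues: "Any new vaginal bleeding (other than normal menstruation), vaginal discharge or pain after dosing should be investigated by vaginal examination". Protocol 9.1.3.2 puts the questions on Days 7 and 14. Protocol 9.1.3.3 (Weeks 8, 12 and 26) lists adverse event monitoring but no gynaecological question. Protocol 12.1.8 makes events of special interest reportable from consent to the End of Study Visit.

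**Analysis.** SAP 8.7 bases all safety analyses on treated subjects. SAP 8.7.1 gives, for events of special interest among others, the "number and percentage of subjects experiencing at least one AE per PT", together with the number of events, and adds: "These summarisations of TEAEs will also be provided for TEAEs occurred during the Acute Exacerbation Phase and for TEAEs occurred during the Stabilisation Phase". SAP 8.7.7 lists the gynaecological assessments without tabulating them. SAP 7.2.4 says endpoints affected by amendments will have sensitivity and subgroup analyses, detailed in the SAP when applicable. Such analyses appear for FEV1 (8.6.2.3), BODE (8.6.4.6) and ECG (8.7.5), but not for this event.

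**The concern.** A percentage for a condition confined to one sex should be taken over that sex. Protocol 9.3.1 admits men and women, so the planned denominator includes people who cannot have the event. Regulators asked for this event to be followed. A reader of the report would take the printed percentage as the risk of the drug, and for women it would be too low.

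The second problem is ascertainment. Women are asked directly in the Acute Exacerbation Phase and, from Day 15, only through general monitoring. Those enrolled before V4.0 were under a protocol without the scheduled questions. The SAP still prints the same table for each phase, side by side, without saying that the two columns were collected differently.

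**Working it through.** **Inputs.** About 270 randomised in a 1:1:1 ratio (SAP 5; Protocol 9.1.1). The plan states no figure for this event, so its sample size serves only to fix the arm denominator. With a difference of 100 mL, SD 230 mL, two-sided alpha 0.05 and 80% power, the normal formula gives 84 per arm against the stated 85. For dropout, 255/0.95 = 268.4, so 269, against about 270. Both reproduce. 270/3 = 90 per arm, taking all randomised subjects as treated. The share of women is not in the documents; call it f.

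**1. Denominator.** With x women affected, W women and N treated subjects in an arm:

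x/N = (x/W) × (W/N) = (percentage in women) × f.

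The understatement factor is 1/f.

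| Assumed f | Women per arm of 90 | Factor 1/f | A 5% risk in women is printed as |
|---|---|---|---|
| 50% | 45 | 2.0 | 2.5% |
| 40% | 36 | 2.5 | 2.0% |
| 30% | 27 | 3.3 | 1.5% |
| 20% | 18 | 5.0 | 1.0% |

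**2. Comparison between arms.** The ratio of two printed percentages is (p1 × f1)/(p2 × f2). It equals p1/p2 only when f1 = f2. With the same 5% risk in women but 50% women in one arm and 40% in another, the table prints 2.5% against 2.0%. Protocol 9.1.1 says the IRT should distribute gender evenly, but Protocol 13.2 describes only blocking by site, so equal shares are not assured.

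**3. Phase.** The Acute Exacerbation Phase is 14 days. The Stabilisation Phase is 26 × 7 − 14 = 168 days, and 168/14 = 12 times as long. Assume a constant hazard λ = 0.02/14 per day, and let s be detection after Day 14 relative to Days 1–14. In women:

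- Acute: 1 − exp(−14λ) = 1.98%.
- Stabilisation: 1 − exp(−168sλ) = 1 − exp(−0.24s).

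| s | Stabilisation Phase % |
|---|---|
| 0.5 | 11.3 |
| 0.25 | 5.8 |
| 0.1 | 2.4 |
| 1/12 | 1.98 |
| 0.05 | 1.2 |

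The later figure is the lower one only if s is below 1/12, about 0.083. A rate per unit of time would fall in proportion to s, but SAP 8.7.1 plans such a rate for pneumonia only.

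**4. Protocol version.** If a share v of women enrolled before V4.0 and none of their events were detected, the percentage keeps a fraction 1 − v of its value. For v = 2%, 5%, 10% or 20%, the relative loss is 2%, 5%, 10% or 20%. The documents do not give v. SAP 8.6.4.6 calls the V2.0/V3.0 group small.

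**The case against.** The strongest reply is that the women-only figure can be rebuilt. SAP 8.7.1 prints counts beside percentages, SAP 8.4.1 tabulates sex by regimen in the Safety population, SAP 8.1.9 puts sex on every listing, and SAP 8.7.1 gives events of special interest their own listing. No safety test is planned (SAP 8.7), and the relative comparison holds if sex is balanced. Table templates are in a separate document (SAP 1) and might carry a sex-specific denominator. All of this is true and limits the harm, but none of it corrects the percentage that the SAP specifies.

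A reader might infer that the reported figure must fall after Day 14 because the questions stop, and that the fall would look like reversibility. The documents do not support this. Events of special interest remain reportable to the End of Study Visit, new symptoms after dosing must be investigated with no end date, and the later window is 12 times longer, so the percentage can rise. SAP 7.2.2.4 assigns phase by onset date, so a lower later count would mean fewer new onsets, not resolution.

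Nor does the lack of a scripted question mean no surveillance. The last dose is on Day 5, and Protocol 9.3.2 gives 8 days for five half-lives, which ends about Day 13. Days 7 and 14 therefore cover most of the exposure window, though later onset remains possible.

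The protocol-version effect is real but bounded by the size of a small subgroup, and SAP 7.2.4 includes the qualifier about applicability.

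**Conclusion.** The point stands on two counts. First, the planned percentage understates the risk in women by 1/f: 2.0- to 5.0-fold for an assumed share of women from 50% down to 20%, and by some amount for any mixed-sex sample. Only the size depends on the assumption. Second, ascertainment differs by phase and by protocol version, so the phase percentages are not directly comparable. The direction and size of that difference cannot be settled from the documents, and the version part is secondary.

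No efficacy conclusion is affected. The between-arm comparison is distorted only if the share of women differs between arms. The correction is still worth making, because this is a named safety endpoint added at a regulator's request and no planned table gives the right percentage.

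**What to change.** In SAP 8.7.1, state that for cervical/vaginal inflammation the denominator is women in the Safety population of each regimen, overall and by phase. Add a footnote that scheduled symptom questions began with protocol V4.0, that after dosing they are set for Days 7 and 14 only, and that later events come from general adverse event monitoring, so the two phases should not be compared directly. Optionally, show the Acute Phase result for women enrolled under V4.0/V5.0, in line with SAP 7.2.4.

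This needs no new data, only SAP wording and one table. The price is a smaller denominator, for example 27 in place of 90 per arm at 30% women, and hence a less precise percentage.

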8.7.2 Clinical laboratory evaluations

Haematology, blood chemistry, and urinalysis will be conducted at Screening, on Days 1, 3, 5, 7, 10 and 14, and at each visit in the Stabilisation Phase.

Haematology, blood chemistry and pregnancy tests done at the Screening visit of the study should be sent to both the local laboratory and central laboratory for analysis. Haematology, blood chemistry and pregnancy done at all other visits of the study should be sent only to the central

laboratory for analysis, with the exception of urine dipstick pregnancy test that should be done at the local laboratory. The following laboratory parameters will be assessed:

- Blood chemistry:
 - Creatinine
 - Blood urea nitrogen [BUN]
 - Fasting serum glucose
 - Aspartate aminotransferase [AST]
 - Alanine aminotransferase [ALT]
 - Gamma-glutamyl transpeptidase
 - Total bilirubin
 - Albumin
 - Chloride
 - Calcium
 - Phosphorous
 - Uric acid
 - Total protein
 - Sodium
 - Potassium.
- Haematology:
 - Red Blood Cell Count [RBC]
 - White Blood Cell Count [WBC]
 - Neutrophils
 - Lymphocytes
 - Monocytes
 - Eosinophils
 - Basophils
 - Haemoglobin
 - Haematocrit
 - Platelets
 - INR (not required during the Stabilisation Phase)
 - Prothrombin time (not required during the Stabilisation Phase).
- Urinalysis:
 - Specific gravity
 - pH
 - Protein
 - Glucose
 - Blood.

- Pregnancy test:
 - Serum β -HCG
 - Urinary pregnancy test.

For the purposes of summarisation in both the tables and listings, all clinical laboratory data will be reported in Standard International (SI) units.

If a lab value is reported using a nonnumeric qualifier e.g., less than (<) a certain value, or greater than (>) a certain value, the given numeric value will be used in the summary statistics, ignoring the nonnumeric qualifier.

Descriptive statistics will be presented for quantitative clinical laboratory parameters for each treatment regimen and time-point. Similarly, changes from baseline will be summarised. Values outside the normal range will be categorised as H (above the normal range) or L (below the normal range) based on the laboratory's reference range and these will be flagged in the individual data listings along with the Investigator's assessment.

In addition, the number and percentages of subjects with laboratory values for liver function and enzymes of clinical concern⁷ as follows will be presented descriptively per treatment regimen during the Acute Exacerbation Phase.

Parameter	Level for clinical concern
ALT	> 1.5 times the upper limit of the normal range (ULN) > 2xULN > 3xULN > 5xULN > 10xULN
AST	> 1.5xULN > 2xULN > 3xULN > 5xULN > 10xULN
Bilirubin Total	> 2xULN > 3xULN
ALT/AST and Bilirubin Total	ALT/AST > 3xULN and Bilirubin Total > 2xULN

Haematology, blood chemistry, pregnancy test results and qualitative urinalysis parameters (protein, glucose and blood) will be listed, including data from scheduled and unscheduled timepoints.

